## **1.0 SPECIFIC AIMS:**

"Women serving in the military are essential components of our Nation's success," Secretary of Veterans Affairs Eric Shinseki acknowledges (2011). "In honor of their service, VA is committed to providing women Veterans with quality care and preparing for their evolving needs." Indeed, women and OEF/OIF/OND Reserve/National Guard (RNG) war Veterans are among the fastest growing groups of new VA users. Women comprise 15% of the armed forces overall and 17% of RNG forces (Meehan, 2006). Of all recently discharged Veterans eligible for VA care, approximately half are RNG members (Deyton & Kang, 2008). RNG members appear to have higher rates of post-deployment mental health (MH) problems, including PTSD, with progressively increasing rates of MH problems at 3 and 12 month follow-up compared to stable rates for active component service members (Thomas et al., 2010). Unfortunately, the effects of military experiences, including combat, post-deployment readjustment, and sexual assault are not yet well characterized in RNG servicewomen. A recent study of both male and female Afghanistan combat Veterans found that around half (56%) report that post-deployment reintegration is difficult (Sayer et al., 2011). Yet, for a variety of reasons (e.g., stigma, prior military assault, VA care perceptions, established care prior to deployment) facilitating access to MH services for RNG OEF/OIF/OND female Veterans with PTSD is challenging and will require new approaches to outreach. Indeed, such approaches are urgently needed to mediate the severity of post-deployment MH conditions, alleviate concerns over MH diagnoses and interrupt the cycle of chronicity found in many with PTSD. A web-based interface tailored to consumer needs has the potential to promote active engagement by Veterans in their health care, a process shown to be effective in civilian populations. Furthermore, researchers have found that when patients are educated about their physical health conditions and treatment alternatives, shared decision-making results in better health outcomes. However, more studies are needed with MH care (Perestelo-Perez et al., 2011). The long-term goals of this project are to: 1) increase RNG servicewomen's knowledge about their own post-deployment adjustment, including PTSD, enhance PTSD self-management while decreasing stigma about readjustment and MH conditions; 2) improve non-VA user RNG servicewomen's willingness to access VA MH care for PTSD and evidence based psychotherapy (EBP); 3) revise an existing web-based interface, which is portable and can interface with My HealtheVet (MHV) and, 4) ultimately enhance RNG servicewomen's engagement with VA and with MHV so that VA non-users will be more likely to access VA care and current users will be more likely to receive the benefit of EBP for PTSD. The immediate goals of this study are 1) to understand female war Veterans' perceptions, preferences and barriers to EBP for PTSD; 2) augment our current web-based interface with this information to incorporate educational interventions specific to EBP for PTSD; and 3) test specific access routes to VA care in order to determine whether a concierge nurse case manager shared decision-making intervention can increase linkages to VA services for PTSD and initiation of EBP initiation for OEF/OIF/OND RNG post-deployment women Veterans compared to a more standard access route (outreach).

**Specific Aim #1: Using focus groups, identify VA enrolled OEF/OIF/OND RNG female war Veterans' perceptions, preferences and identified barriers and facilitators to accessing VA MH services and EBP (including cognitive processing therapies and prolonged exposure therapy) for PTSD.**

Hypothesis 1.a: OEF/OIF/OND RNG servicewomen with PTSD who differ in factors associated with access to care based on Aday and Andersen's (1974) model will identify different barriers and facilitators to VHA services for PTSD including EBP.

Hypothesis 1.b: With improved understanding of the consumer's perceptions of, or experiences with VA mental health care for PTSD and EBP, we can further tailor our existing web-based educational interface to better address the gap between PTSD care need and EBP access.

**Specific Aim # 2: To evaluate the participants' perceptions of and satisfaction with the revised web-based interface and to evaluate and test differences in VHA initiation and use for those who screen positive for PTSD by randomly assigned route: 1) Study concierge nurse case manager (NCM) or 2) existing outreach.**

Hypothesis 2.a: Web-based interface is a successful way to improve Veterans' post-deployment health education and VA access as demonstrated by web-intervention satisfaction survey and subsequent enrollment.

Hypothesis 2.b: Use of a nurse case manager to promote shared decision-making regarding PTSD services and EBPs will result in increased use of MH care and initiation of EBP for PTSD compared to outreach counselors.

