## Phase 2:

Phase 2 of the study will involve 5 Steps: 1) Web-based pre-interface survey; 2) web-based screening and tailored education and resource links; 3) post-interface satisfaction and intended care survey; 4) random assignment to concierge nurse case manager versus in place OEF/OIF/OND outreach workers 5) post-intervention follow-up.

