All contact professionals and PBRN/CREATE sites will be involved prior to study initiation, educated about this study, and engaged in facilitating outreach and care. It is noteworthy that our research team's studies that use focus groups and telephone interviews with more intensive questions about sexual assault in RNG populations have not resulted in any subsequent clinical emergencies. Women who have no positive screens will be able to access the same educational information and web links if they choose to. The web-based post-screening survey immediately following the screening and education interface will be revised from our original web-and semi-structured survey to include satisfaction with information about VA MH and EBP for PTSD that they receive in the web education intervention. We will also repeat the check-list of barriers and facilitators to VA MH care and to PTSD EBP tailored from the participant's prior responses to determine if the web-based intervention altered their perceptions. We will also query those who are PTSD positive and who are not engaged in PTSD EBP and other MH care whether they intend to seek care as a result of their participation and why or why not. Participants will be reimbursed \$30.00 for the time and effort to complete the web-interface and pre-and post-surveys. If they complete the web-interface and pre and post surveys within two weeks following their initial postal or e-mail invitation then they will receive an additional \$10.00. In order to receive subject reimbursement, participants will be asked to provide their names and social security number to the coordinator through a toll-free number. These data and linkage study ID number will be maintained in a locked and limited access research network electronic file behind the VA firewall. With these subject identifiers we are able to access participant VA records, given subject IRB consent. VA health services utilization will be obtained from all consenting participants in this phase of the study, including initiation of mental health services (either in primary care or specialty care) and extent of participation in EBP. Participation will be measured by self-report of EBP engagement, type, and number of sessions. This will be validated by VA electronic chart review.

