local VA mental health and PTSD evaluation and treatment in the Veteran's locale, or 2) OEF/OIF/OND outreach coordinators in place at every VA. A toll-free number will be provided to participants assigned to the NCM with information that they can initiate contact and that they otherwise will be telephoned by the NCM within 2 weeks following completion of the post-intervention survey. Pharos Innovations (web-interface developer) will provide immediate notification to the study NCM of participants who are assigned to each group and she will be able to access web results of participant study screens. Upon telephone contact with the participant, the concierge NCM will engage the patient and by telephone administer a 17 item PTSD Checklist (PCL) developed by the National Center for PTSD to assess the presence of DSM-IV criteria for PTSD. She will use the PCL-S that allows identification of a specific traumatic event. This will assist with PTSD validation and allow for individualized referral. The NCM will then follow shared decision making protocols for specific domains (Joosten et al., 2008). Domains include (pending focus group augmentation): 1) Actively reporting all information and PTSD treatment possibilities to the patient/consumer. The NCM can recommend an option but PTSD treatment and therapy are decided jointly; 2) Encourages the patient to discuss preferences and form their own judgment regarding the harms and benefits of PTSD treatment/EBP options; 3) Makes sure that the information exchange is two-way between patient and NCM; 4) NCM informs partner or key family members who the Veteran includes in the telephone interface in the PTSD treatment decision-making process; 5) Informs Veteran about routes of access to VA or if already enrolled ways to access PTSD EBP and facilitates as needed and actively links with care; and 6) Addresses barriers and facilitators checked by the Veteran on her web-based interface and assists the Veteran in addressing these (e.g., education regarding night clinics, transportation). The NCM will review all PTSD treatment options, including pharmacotherapy and site specific options, e.g. unique groups. Subjects will be educated about the efficacy, risks and benefits, duration of each treatment option. Participants are welcome to re-contact the NCM on our toll free number for further questions and assistance with care initiation or transitions during the duration of the study. However, the NCM will not initiate further follow-up. The study concierge NCM, [name], R.N., M.S. will build on her own skills as a career Army nurse and prior OEF/OIF outreach counselor. She will be trained in the intervention protocol by PI ([name]) and co-I (MV) who are MH care professionals with unique clinical and research expertise specific to this intervention. NCM model fidelity and tools developed (manual, check lists for PTSD and MH utilization, satisfaction) will be guided by consultant [name], who has expertise specifically useful to this with his work with the VA's Translating Initiatives for Depression into Effective Solutions (TIDES) project in his QUERI implementation expert role. It should be noted that the NCM will use VA/DoD Clinical Practice Guidelines for The Management of PTSD (<http://www.healthquality.vagov>) for assistance with patient education, management, and tracking utilization specific to EBP but also other PTSD treatment interventions documented on the treatment checklist tracking utilization in post-intervention follow-up. Use of PBRN and CREATE study sites will allow NCM interface with PC, WHC, and MH teams already sophisticated about and engaged in evolving women's health care and research. This existing infrastructure of relationships and resources will facilitate the successful implementation and evaluation of the NCM linkage intervention. Traditional OEF/OIF/OND outreach counselors educate returning Veterans about their VA eligibility, facilitate enrollment and subsequent appointment scheduling. The NCM will have a complementary role in that her interventions will be specific to PTSD and EBP treatment.

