
**Post-Intervention Follow-up:** Women who screened positive for PTSD and were randomly assigned to NCM or usual OEF/OIF/OND outreach VA PTSD treatment access route will be contacted by the study research coordinator by telephone at 6 and 12 months following web-based interface. The study coordinator will use an IRB approved call contact protocol varying times of day and days of week (used successfully by this team) and ask willing participants brief questions using computer-assisted telephone interview data collection.

Satisfaction with access route and consumer feedback regarding these will be assessed. Those who did not engage in VA MH or EBP will be queried to determine if they have sought non-VA care for their PTSD, including EBP, and current factors influencing needed PTSD services. Using DMDC data, this group will be compared to VA users with regard to access and military characteristics (e.g. rank, number of deployments) in addition to web-based screening data. Women who did engage in VA MH or EBP will be asked about their experiences and satisfaction with EBP and VA care. VA service use will be validated by electronic records. Participants will be also asked about their current satisfaction with the effectiveness of the web-based interface and subsequent utilization of educational links. Non-users will be asked about current barriers to VA and MH services and again offered assistance with access to VA care and EBP if desired. We will use DMDC data to provide comparison to women who initially screened positive for PTSD. Women completing the 6 and 12 month follow-up interviews will be reimbursed \$15.00 for each completed interview.

Sample Size Analysis and Statistical Plan: The pre- and post-satisfaction surveys integrated within the Phase 2 web-based interface will be analyzed to estimate prevalence of post-deployment mental health concerns, pre-interface knowledge and current health care use, and post-interface knowledge, satisfaction, and participants' intentions to seek services for mental health care needs identified through the web-based screening.

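### Hypothesis 2.a takes later enrollment as showing that the web interface improves VA access, but no group without the interface and no background enrollment rate is planned, so enrollment cannot be credited to the web

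*Combined protocol and SAP*

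**What the plan says.** Hypothesis 2.a, in 1.0 Specific Aims, states that the interface succeeds in improving education and VA access, "as demonstrated by web-intervention satisfaction survey and subsequent enrollment". Aim 2, which it serves, is more modest about the web. It promises to evaluate perceptions of and satisfaction with the interface, and reserves testing for the two access routes.

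The Phase 2 section lists five steps. The pre-survey, the screening and education, and the post-survey come first. Step 4 is "random assignment to concierge nurse case manager versus in place OEF/OIF/OND outreach workers", and it applies only to women who screen positive for PTSD.

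The section on random assignment describes the two routes. On outreach: "Traditional OEF/OIF/OND outreach counselors educate returning Veterans about their VA eligibility, facilitate enrollment and subsequent appointment scheduling". The NCM "facilitates as needed and actively links with care". Under Post-Intervention Follow-up, the randomised women "will be contacted by the study research coordinator by telephone at 6 and 12 months following web-based interface", and those not using VA services are "again offered assistance with access to VA care and EBP if desired".

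For records, the Phase 2 Intervention Process says that "VA health services utilization will be obtained from all consenting participants in this phase of the study". The statistical plan describes the web analysis as estimates of prevalence, knowledge, current care use, satisfaction and "intentions to seek services for mental health care needs identified through the web-based screening". It names no enrollment measure, denominator or time window.

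**The concern.** To say that something improves access is to claim an effect, and the hypothesis names enrollment as part of the proof. An effect on enrollment needs some idea of what enrollment would have been without the interface, and the plan supplies none. As written, any woman who enrolls after using the interface counts in its favour. That includes women who would have enrolled anyway, women more inclined to seek care because they chose to respond, and women linked to care by the NCM.

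Background uptake is likely to matter here. The protocol describes these Veterans as among the fastest growing groups of new VA users, and participants are within 24 months of return from deployment. At stake is an unsupported statement in the study report that the web interface improves access.

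**Working it through.** **Planned numbers, reproduced.** From Sample Size: 2,000 women requested × 20% response = 400, and 400 × 30% screening positive = 120. The statistical plan uses the same split, 120 PTSD-positive and 280 PTSD-negative. Shares: 120/400 = 30% and 280/400 = 70%.

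**Is any group free of the interface?**
- By the order of steps in Phase 2, all 400 complete the interface before assignment. Web-free participants: 0 of 400.
- The nearest candidates are the 2,000 − 400 = 1,600 refusals and non-responders. The Sampling paragraph compares them with participants on sociodemographic and military data, to judge generalizability. VA utilization is obtained only for consenting participants, so enrollment is not compared.
- The analyses in the statistical plan are descriptive estimates, paired mean differences, PTSD-positive versus PTSD-negative, and NCM versus outreach. None compares web with no web, and no historical or external enrollment rate is cited.

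**What enrollment after the interface would mix, by group.**

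| Group | Planned n | Mixed with any web effect |
|---|---|---|
| PTSD-negative | about 280 | background uptake, self-selection |
| PTSD-positive, NCM | about 60* | the same, plus active linkage by the NCM and help offered at the 6-month call |
| PTSD-positive, outreach | about 60* | the same, plus help offered at the 6-month call; assignment to outreach less clearly |

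*The allocation ratio is not stated; 1:1 is assumed.

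Outreach is marked less clearly for two reasons. The protocol treats it as the existing service at every facility. The interface itself also gives women who screen positive on any condition links to outreach staff, so some enrollment through outreach is a path the web is meant to open. Help offered at the 12-month call falls at the end of a 12-month window and could hardly affect a count taken over it.

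**Size of the distortion.** It cannot be computed. The documents give no enrollment rate, background rate or route effect on enrollment.

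**Precision of the descriptive report proposed below.** This measures what the remedy can deliver, not the defect. Wilson 95% half-width = z/(1 + z²/n) × √[p(1−p)/n + z²/(4n²)], with z = 1.96. Assumed: 50% to 90% of women not VA-enrolled beforehand, 10% to 30% of those newly enrolling, 60 per arm.

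| Denominator | p = 10% | p = 30% |
|---|---|---|
| PTSD-negative, 0.9 × 280 = 252 | 3.7 points | 5.6 points |
| PTSD-negative, 0.5 × 280 = 140 | 5.0 | 7.5 |
| Per arm, 0.9 × 60 = 54 | 8.2 | 11.9 |
| Per arm, 0.5 × 60 = 30 | 11.1 | 15.6 |

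**The case against.** The best defence is that the plan never sets out to test a web effect on enrollment. Aim 2 promises perceptions and satisfaction, and the statistical plan estimates knowledge, satisfaction and intentions. Hypothesis 2.a also has other support: the barrier and facilitator checklist is repeated after the interface, and PTSD-positive women not in care are asked whether they intend to seek it as a result of taking part. Both come before assignment. This stands, and it is why the education and satisfaction half is left alone. It does not rescue the access half, because the hypothesis still names enrollment as the demonstration and the analysis text is silent on enrollment.

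A second defence is that enrollment is not defined and might mean joining the access-route study, since the summary of preliminary work speaks of interest in enrolling in that study. The ambiguity is real. The mention of VA access in the hypothesis favours VA enrollment, and study enrollment would not measure VA access at all. Either reading calls for a definition.

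A third concerns outreach. A reader might infer that all enrollment helped by outreach is wrongly credited to the web. The documents do not support that, for the reasons given with the table of groups. The contrast with the 280 PTSD-negative women is not clean either. In the pilot fewer than 1% screened negative on everything, so most of the 280 would probably receive outreach links too. The clear added intervention is the NCM.

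**Conclusion.** The concern holds for the access half of Hypothesis 2.a. With 0 of 400 women outside the interface and no background rate, later enrollment cannot be attributed to the web in any group. Among the roughly 120 PTSD-positive women, the NCM and the 6-month offer of help add to the difficulty. The conclusion rests on the order of steps and the listed analyses. It needs no assumption about effect sizes; only the precision figures rest on assumed values.

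A reader might infer more than this. The randomised NCM-outreach comparison is not compromised, since both arms receive the interface. Nothing here shows that the interface has no effect on access; the design simply cannot tell. No section makes adoption of the interface depend on Hypothesis 2.a, so the harm is an unsupported claim in the report. The wording should be changed, and the change is cheap.

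**What to change.** 1. Remove enrollment as the demonstration that the web improves access. Restate that half of 2.a as descriptive, in line with Aim 2 and the statistical plan: satisfaction, knowledge, perceptions and intention to seek care.
2. Define enrollment as new VA enrollment among women not VA-enrolled before the interface. Take prior status from VA records or from one added pre-survey item. The present pre-survey asks about utilization, and a woman who does not use VA care may already be enrolled.
3. Count it from VA records over one fixed window from interface completion, the same for all groups, for example 12 months. The 6- and 12-month interviews reach only the PTSD-positive 30%, so they cannot supply a common window.
4. Report it with 95% CIs separately for PTSD-negative women, outreach and NCM. Present no pooled or before-after rate as a web effect.
5. Describe any NCM-outreach difference in enrollment as a randomised route comparison under Aim 2. It is not evidence for the web, and it is not a Hypothesis 2.b outcome, since 2.b names mental health care use and initiation of evidence-based psychotherapy.

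The cost is half a hypothesis reworded, one definition with a window, and a records check or one survey item. No new arm, participants or visits are needed. It relies on the consented record access already planned, assuming those records show enrollment status and date. The downside is a more modest claim and smaller denominators. Under the assumptions above, 95% half-widths would be 3.7 to 7.5 points in PTSD-negative women and 8.2 to 15.6 points per arm.

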## RESEARCH PLAN

### 2.0 BACKGROUND

#### Women Frequently Choose not to use VHA Care:

Many women Veterans do not know that women's health care is even available in the VHA and are concerned with the quality of care that exists (Washington et al., 2007). Women exposed to combat are less likely to use VHA care because they believe it is male-oriented. When they do use VA care, they have lower opinions of VA health care facilities and more problems with doctors and staff (Kelly et al., 2008). High rates of military sexual trauma (MST) are reported by women pre-OEF/OIF and more recently in RNG populations with 15% of VA enrolled female Iraq/Afghanistan Veterans screening MST positive. MST is a major contributor to PTSD (Sadler et al., 2004; Street et al., 2007; Suris et al., 2004, Booth et al., 2011). These women are significantly less likely to believe they are safe from sexual harassment at the VHA compared to non-traumatized peers (Mengeling et al., 2011). Despite high use of services, women with MST are more likely to have less satisfaction with and poorer perceptions of VHA care than those without MST (Kelly et al., 2008).

